5.15 Time and Events Table

	Screening				End of Treatment ⁴	SOC Follow- up ⁵								
Procedure	(Within 6 weeks of Day 1)	C1 D1	C1 D8	C1 D15	C2 D1	C2 D8	C3 D1	C4 D1	C5 D1	C6 D1	Even Cycles	Odd Cycles	30-days after drug discontinuation, +/- 7 days	Every 12 Weeks
Informed Consent ¹	Х													
Tempus HRD ¹¹	Х													
Physical Exam (includes Medical history)	х	х	х	х	х		х	х	х	х	X	×	Х	Х
Vitals ²	Х	Х	Х	Х	Х		Х	Х	Х	Х	Х	Х	Х	Х
ECOG Performance Status	х	х			Х		Х	Х	Х	Х	Х	Х	Х	Х
Hematology ⁸	Х	Х	Х	Х	Х	Х	Х	Х	Х	Х	Х	Х	Х	Х
Chemistry ⁸	Х	Х	Х	Х	Х	Х	Х	Х	Х	Х	Х	Х	Х	Х
Tumor markers (CA2729, CEA, CA- 125)		as per standard of care, at the investigator's discretion												
T3 Free, T4 Free, TSH ⁸	Х				Х			Х		Х	Х		Х	
Coagulation (PT, INR, aPTT)	X ⁸													
Urine or serum pregnancy test	X ₈													
EKG	Х													
Archival Tumor Tissue Collection	X ¹⁰													
CT Scan (Chest, Abdomen, Pelvis) and/or MRI	×		As clinically indicated (or every 9 weeks for Response assessment)						Х					
Whole body Bone Scan	Х		As clinically indicated											

Procedure	Screening (Within 6 weeks of Day 1)	Treatment Phase (+/- 3 days) ³											End of Treatment ⁴	SOC Follow- up ⁵
		C1 D1	C1 D8	C1 D15	C2 D1	C2 D8	C3 D1	C4 D1	C5 D1	C6 D1	Even Cycles	Odd Cycles	30-days after drug discontinuation, +/- 7 days	Every 12 Weeks
Adverse Event Assessment	Х		Х	Х	X		Х	Х	Х	Х	х	Х	Xe	X ⁶
Concomitant Medications	Х		Х	Х	X		Х	Х	Х	Х	Х	Х	Х	Х
Pembrolizu mab Administrati on		x			х		х	х	х	Х	Х	Х		
Olaparib Administrati on and Olaparib Compliance Diary			Daily ⁷											

¹Informed consent may be obtained within 6 weeks of Cycle 1, Day 1

²Vital signs to include temperature, pulse, respiratory rate, weight, and blood pressure. Height will be measured at Screening only.

³Study treatment is up to 35 administrations of pembrolizumab (approximately two years).

⁴If subject discontinues drug due to progression, the End of Treatment visit (30 days after study treatment discontinuation, +/- 7 days) will end their participation in the study and will not be followed thereafter.

⁵Subjects who discontinue trial treatment for a reason other than disease progression will move into the Follow-Up Phase and should be assessed every 12 weeks (56 ± 7 days) by radiologic imaging to monitor disease status, per standard of care for up to two years of total study participation.

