⁶SAEs and ECIs should be reported for 90 days after last pembrolizumab dose or until new anticancer treatment is initiated, but for a minimum of 30 days, whichever occurs first.

⁷Olaparib will be dispensed each cycle day 1 (each cycle=3 weeks). Subjects will be given an olaparib dosing diary at Cycle 1 Day 1, and at Day 1 of each subsequent cycle while taking olaparib. The completed diary will be collected at the next cycle Day 1. Olaparib dosing must begin within 3 days of pembrolizumab C1D1.

⁸Laboratory tests for screening should be performed within 10 days prior to the first dose of pembrolizumab. After Cycle 1, pre-dose laboratory procedures can be conducted up to 72 hours prior to dosing. Results must be reviewed by the investigator or qualified designee and found to be acceptable prior to each dose of trial treatment.

⁹ Female subjects of childbearing potential should have a negative urine or serum pregnancy prior to study registration and re-tested within 72 hours prior to receiving the first dose of pembrolizumab. If the urine test is positive or cannot be confirmed as negative, a serum pregnancy test will be required.

¹⁰The pre-treatment archival tumor tissue sample for correlative studies may be sent to QualTek any time after eligibility verification.

¹¹ Tempus testing will be performed only on patients who do not otherwise qualify based on BRCA status. Archival tumor tissue plus a normal matching sample (blood preferred) will be collected and shipped to Tempus. De-identified clinical data elements will be shared with Tempus as specified in the master

agreement (may be sent after screening).

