6.1.2 Events of Clinical Interest

Selected non-serious and serious adverse events are also known as Events of Clinical Interest (ECI) and must be recorded as such on the Adverse Event case report forms/worksheets and reported within 2 working days from time of PI acknowledgment to Merck Global Safety. (Attn: Worldwide Product Safety; [contact])

Events of clinical interest for this trial include:

- 1. an overdose of pembrolizumab that is not associated with clinical symptoms or abnormal laboratory results. For purposes of this study, an overdose of pembrolizumab will be defined as any dose of 1,000 mg or greater (≥5 times the indicated dose). No specific information is available on the treatment of overdose of pembrolizumab. In the event of overdose, the participant should be observed closely for signs of toxicity. Appropriate supportive treatment should be provided if clinically indicated. If an adverse event(s) is associated with ("results from") the overdose of a Merck product, the adverse event(s) is reported as a serious adverse event, even if no other seriousness criteria are met.
- 2. an elevated AST or ALT lab value that is greater than or equal to 3X the upper limit of normal and an elevated total bilirubin lab value that is greater than or equal to 2X the upper limit of normal and, at the same time, an alkaline phosphatase lab value that is less than 2X the upper limit of normal, as determined by way of protocol-specified laboratory testing or unscheduled laboratory testing.*

*Note: These criteria are based upon available regulatory guidance documents. The purpose of the criteria is to specify a threshold of abnormal hepatic tests that may require an additional evaluation for an underlying etiology.

ECIs (both non-serious and serious adverse events) identified in this guidance document from the date of first dose through 90 days following cessation of treatment, or 30 days after the initiation of a new anticancer therapy, whichever is earlier, need to be reported within 24 hours to the Sponsor and within 2 working days to Merck Global Safety. (Attn: Worldwide Product Safety; [contact]), regardless of attribution to study treatment, consistent with standard SAE reporting guidelines.

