6.2 Steps to Determine If an Adverse Event Requires Expedited Reporting

- Step 1: Identify the type of adverse event using the NCI Common Terminology Criteria for Adverse Events (CTCAE v4).
- Step 2: Grade the adverse event using the NCI CTCAE v4.

Step 3: Determine whether the adverse event is related to the protocol therapy Attribution categories are as follows:

- Definite The AE *is clearly related* to the study treatment.
- Probable The AE is likely related to the study treatment.
- Possible The AE *may be related* to the study treatment.
- Unrelated The AE is clearly NOT related to the study treatment.

Note: This includes all events that occur within 30 days of the last dose of protocol treatment. Any event that occurs more than 30 days after the last dose of treatment and is attributed (possibly, probably, or definitely) to the agent(s) must also be reported accordingly. SAEs and ECIs should be reported for 90 days after last pembrolizumab dose or until new anticancer treatment is initiated, but for a minimum of 30 days, whichever occurs first.

Step 4: Determine the prior experience of the adverse event.

Expected events are those that have been previously identified as resulting from administration of the agent. An adverse event is considered unexpected, for expedited reporting purposes only, when either the type of event or the severity of the event is not listed in the current known adverse events listed in:

- the current known adverse events listed this protocol;
- the drug package insert; and/or
- the current Investigator's Brochure

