6.4 Reporting Requirements for Adverse Events

6.4.1 Expedited Reporting to PI

The Principal Investigator must be notified within 24 hours of learning of any serious adverse events, regardless of attribution, occurring during the study or within 30 days of the last administration of the study drug. SAEs and ECIs should be reported for 90 days after last pembrolizumab dose or until new anticancer treatment is initiated, but for a minimum of 30 days, whichever occurs first.

Phone Number for Expedited Reporting: [contact]

Alternate Phone Number for Expedited Reporting: [contact]

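### The ECI reporting window in 6.1.2 contradicts the SAE/ECI window stated elsewhere, and patients who stop for progression leave the study well before day 90

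*Combined protocol and SAP*

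**What the plan says.** Four parts of the protocol bear on how long serious events and ECIs are collected after treatment.

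- **Main rule (5.15 footnote 6, repeated in 6.2, 6.3 and 6.4.1).** "SAEs and ECIs should be reported for 90 days after last pembrolizumab dose or until new anticancer treatment is initiated". The sentence goes on to set a 30-day floor and closes on an earliest-date clause: "or until new anticancer treatment is initiated, but for a minimum of 30 days, whichever occurs first".
- **ECI rule (6.1.2).** Reporting runs from first dose "through 90 days following cessation of treatment, or 30 days after the initiation of a new anticancer therapy, whichever is earlier", whatever the attribution.
- **30-day statements.** Section 6.4.1 first asks for notification of SAEs, whatever the attribution, "occurring during the study or within 30 days of the last administration of the study drug", and then gives the 90-day rule in its next sentence. Section 6.2 has the same pattern: "This includes all events that occur within 30 days of the last dose of protocol treatment", then an open-ended duty to report later events attributed to the agents, then the 90-day rule.
- **Follow-up after progression (5.15 footnote 4; 4.6).** The End of Treatment visit, 30 days after discontinuation with a margin of 7 days either way, "will end their participation in the study and will not be followed thereafter". Section 4.6 agrees, giving about one month. Patients who stop for any other reason move to 12-weekly follow-up, where adverse event assessment is scheduled.

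Section 4.2.1 states that immune-related events can first appear months after dosing has stopped.

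**The concern.** Site staff applying 6.1.2 and staff applying footnote 6 would close the ECI window on different days for the same patient. A 90-day window is also hard to honour in a patient who left the study at about day 30. Both matter because the trial has no toxicity stopping rule: 9.2 bases early stopping on response. Safety oversight by the principal investigator and the monitoring committee (10.5.1) therefore rests on the events that reach them. As scheduled, the chance that a late event reaches them depends on why the patient stopped treatment.

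**Working it through.** The plan gives no figure to reproduce. The check puts the rules side by side as day counts.

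**Inputs.** T is the day new anticancer therapy starts, counted from the last pembrolizumab dose. E is the day of the End of Treatment visit: 30 ± 7, so 23 to 37. Both drugs are assumed to stop on the same day, so that the two start points coincide.

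**1. End of the ECI window.** Footnote 6, on its workable reading (90 days or new therapy, whichever is earlier, never under 30 days), gives A = min(90, max(30, T)). Section 6.1.2 gives B = min(90, T + 30).

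| T | A (footnote 6) | B (6.1.2) | B − A |
|---|---|---|---|
| 14 | 30 | 44 | 14 |
| 30 | 30 | 60 | 30 |
| 40 | 40 | 70 | 30 |
| 60 | 60 | 90 | 30 |
| 75 | 75 | 90 | 15 |
| 90 or later, or none | 90 | 90 | 0 |

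The difference is T days up to day 30, 30 days from day 30 to day 60, and 90 − T from day 60 to day 90.

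**2. Footnote 6 read literally.** If the earliest-date clause covers all three terms, the window is min(90, T, 30). This never exceeds 30, so the 90 days would have no effect.

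**3. Start point.** Footnote 6 counts from the last pembrolizumab dose and 6.1.2 from cessation of treatment. Under 4.5, pembrolizumab is capped at 35 administrations while olaparib runs to progression or unacceptable toxicity. The two start points can therefore separate.

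**4. Days without scheduled contact after progression, no new therapy.** 90 − E:
- E = 23: 67 days, 67/90 = 74%
- E = 30: 60 days, 60/90 = 67%
- E = 37: 53 days, 53/90 = 59%

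**5. Effect of early new therapy.** Under footnote 6 the gap is A − E. With T at or before day 30, A = 30. The gap is then 30 − 23 = 7 days at most, and zero for a visit on day 30 or later. Under 6.1.2 with T = 30, the ECI window runs to day 60, so a day-30 visit leaves 30 days.

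**6. How many patients footnote 4 might touch (assumption only).** The documents give no expected share stopping for progression. The only PFS figure is the background median of 6 months for PARP inhibitors (1.1). With exponential PFS and no other reason for stopping, the share progressing by 24 months is 1 − 0.5^(24/6) = 94%. Letting the median run from 4 to 12 months, and competing discontinuation (taken alone) from 0 to 40% by 24 months, the range is 62% to 98%.

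**The case against.** The strongest reply has five parts.

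- **Late related events are already reportable.** Section 6.2 sets no end date for attributed events beyond 30 days, and 6.3 sends related events found in the medical record after End of Treatment to the case report form. Section 6.4.5 requires outcome follow-up of SAEs. A recognised immune-related event is an attributed event, so the duty to report it exists. This stands, and it limits the point. However, these rules are passive. The first two exclude unattributed SAEs and ECIs, which 6.4.1 and 6.1.2 also require, and the third applies only to SAEs already known.
- **The main rule is one sentence with a workable reading.** This also stands. The 90 days, the new-therapy cut-off and the 30-day minimum are parts of one rule, stated consistently in four places, and should not be counted as separate conflicts. The 30-day text in 6.4.1 can be read as a general rule with an extension, but the section does not say so.
- **The rule of 30 days after new therapy covers ECIs only.** Correct. Section 6.1.2 lists two ECIs: a pembrolizumab overdose without symptoms, and a combination of liver-test values. The day 40 versus day 70 example does not apply to SAEs in general.
- **Progressing patients often start new therapy, which shortens the gap.** Correct under footnote 6, as step 5 shows.
- **Safety is not a listed objective, and section 9 plans no comparison of event rates in this 20-patient single-arm pilot.** Correct. Patients stopping for other reasons would have only about one further scheduled visit inside 90 days. The consequence is for safety oversight and description; the primary analysis is unaffected.

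A reader might infer that late immune events will be missed in most patients. The documents do not support that. They give no late-event rate and no share stopping for progression, only a patient who has a late event can have one missed, and related events remain reportable. The change-log entry for version 9 on removing an erroneous footnote 6 does not dispose of the point either: the current text still carries the sentence in four places.

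**Conclusion.** The point holds as two internal contradictions. First, 6.1.2 and footnote 6 give different ECI end dates whenever new therapy starts before day 90, by up to 30 days, and they use different start points. The 30-day and 90-day statements in 6.4.1, and the wording of the floor, add ambiguity. Second, footnote 4 and 4.6 end follow-up after progression at about day 30, against a 90-day reporting window. This leaves 53 to 67 days (59% to 74%) without scheduled contact, on the assumptions that both drugs stop together and no new therapy starts. The gap falls to about zero under footnote 6 if new therapy starts by day 30, and it is shorter under that rule if olaparib stops after the last infusion.

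Capture of late SAEs and ECIs may therefore be incomplete among patients who progress, probably the larger group under the assumptions in step 6. How many events would be missed cannot be computed from the documents. The change is worth making because it is cheap and the protocol itself expects late immune-related events.

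**What to change.** Reconcile 5.15 footnote 6, 6.1.2, 6.2, 6.3 and 6.4.1 to one SAE/ECI reporting window, with one start point and one end condition, and state how the 30-day minimum interacts with new therapy. Which window to adopt is for the sponsor and investigator; this review proposes none. Then amend footnote 4 and 4.6 so that patients who stop for progression have a phone or chart check for SAEs and ECIs at the end of that window, whatever the attribution. The cost is a wording amendment plus one brief contact or chart review per patient, in a trial of 20. No treatment or imaging schedule changes.

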5.16 Removal of Subjects from Study

Patients can be taken off the study treatment and/or study at any time at their own request, or they may be withdrawn at the discretion of the investigator for safety, behavioral or administrative reasons. The reason(s) for discontinuation will be documented and may include:

- **5.16.1** Patient voluntarily withdraws from treatment (follow-up permitted);
- **5.16.2** Patient withdraws consent (termination of treatment and follow-up);
- **5.16.3** Patient is unable to comply with protocol requirements;
- **5.16.4** Patient experiences toxicity that makes continuation in the protocol unsafe;
- **5.16.5** Treating physician judges continuation on the study would not be in the patient's best interest:
- **5.16.6** Patient becomes pregnant (pregnancy to be reported along same timelines as a serious adverse event).

6.0 ADVERSE EVENTS

6.1 Definitions

6.1.1 Definition of Adverse Event

Adverse Event (AE or Adverse Experience): Any untoward medical occurrence associated with the use of a drug in humans, whether or not considered drug related. Therefore, an AE can be ANY unfavorable and unintended sign (including an abnormal laboratory finding), symptom, or disease temporally associated with the use of a medicinal (investigational) product, whether or not considered related to the medicinal (investigational) product (attribution of unrelated, unlikely, possible, probable, or definite). AE's will be collected once the consent is signed and treatment is initiated.

6.1.2 Events of Clinical Interest

Selected non-serious and serious adverse events are also known as Events of Clinical Interest (ECI) and must be recorded as such on the Adverse Event case report forms/worksheets and reported within 2 working days from time of PI acknowledgment to Merck Global Safety. (Attn: Worldwide Product Safety; [contact])

Events of clinical interest for this trial include:

- 1. an overdose of pembrolizumab that is not associated with clinical symptoms or abnormal laboratory results. For purposes of this study, an overdose of pembrolizumab will be defined as any dose of 1,000 mg or greater (≥5 times the indicated dose). No specific information is available on the treatment of overdose of pembrolizumab. In the event of overdose, the participant should be observed closely for signs of toxicity. Appropriate supportive treatment should be provided if clinically indicated. If an adverse event(s) is associated with ("results from") the overdose of a Merck product, the adverse event(s) is reported as a serious adverse event, even if no other seriousness criteria are met.
- 2. an elevated AST or ALT lab value that is greater than or equal to 3X the upper limit of normal and an elevated total bilirubin lab value that is greater than or equal to 2X the upper limit of normal and, at the same time, an alkaline phosphatase lab value that is less than 2X the upper limit of normal, as determined by way of protocol-specified laboratory testing or unscheduled laboratory testing.*

*Note: These criteria are based upon available regulatory guidance documents. The purpose of the criteria is to specify a threshold of abnormal hepatic tests that may require an additional evaluation for an underlying etiology.

ECIs (both non-serious and serious adverse events) identified in this guidance document from the date of first dose through 90 days following cessation of treatment, or 30 days after the initiation of a new anticancer therapy, whichever is earlier, need to be reported within 24 hours to the Sponsor and within 2 working days to Merck Global Safety. (Attn: Worldwide Product Safety; [contact]), regardless of attribution to study treatment, consistent with standard SAE reporting guidelines.

Subjects should be assessed for possible ECIs prior to each dose. Lab results should be evaluated and subjects should be asked for signs and symptoms suggestive of an immune-related event. Subjects who develop an ECI thought to be immune-related should have additional testing to rule out other etiologic causes. If lab results or symptoms indicate a possible immune-related ECI, then additional testing should be performed to rule out other etiologic causes. If no other cause is found, then it is assumed to be immune-related.

6.1.2.1 Olaparib Overdose

There is currently no specific treatment in the event of overdose with olaparib and possible symptoms of overdose are not established.

Olaparib must only be used in accordance with the dosing recommendations in this protocol. Any dose or frequency of dosing that exceeds the dosing regimen specified in this protocol should be reported as an overdose. The maximum tolerated dose is 300mg twice daily (tablet).

Adverse reactions associated with overdose should be treated symptomatically and should be managed appropriately.

For overdoses associated with a SAE, the standard reporting timelines apply, see Section 6.4. For other overdoses, reporting must occur within 30 days.

6.1.3 Severity of Adverse Events

All non-hematologic adverse events will be graded according to the NCI Common Terminology Criteria for Adverse Events (CTCAE) version 4.0. The CTCAE v4 is available at http://ctep.cancer.gov/reporting/ctc.html

If no CTCAE grading is available, the severity of an AE is graded as follows:

- Mild (grade 1): the event causes discomfort without disruption of normal daily activities.
- Moderate (grade 2): the event causes discomfort that affects normal daily activities.
- Severe (grade 3): the event makes the patient unable to perform normal daily activities or significantly affects his/her clinical status.
- Life-threatening (grade 4): the patient was at risk of death at the time of the event.
- Fatal (grade 5): the event caused death.

6.1.4 Serious Adverse Events

A "serious" adverse event is defined in regulatory terminology as any untoward medical occurrence that:

· Results in death.

If death results from (progression of) the disease, the disease should be reported as event (SAE) itself.

Is life-threatening.

(the patient was at risk of death at the time of the event; it does not refer to an event that hypothetically might have caused death if it were more severe).

- Requires in-patient hospitalization or prolongation of existing hospitalization for ≥ 24 hours.
- Results in persistent or significant disability or incapacity.
- Is a congenital anomaly/birth defect
- Is an important medical event

Any event that does not meet the above criteria, but that in the judgment of the investigator jeopardizes the patient, may be considered for reporting as a serious adverse event. The event may require medical or surgical intervention to prevent one of the outcomes listed in the definition of "Serious Adverse Event".

For example: allergic bronchospasm requiring intensive treatment in an emergency room or at home; convulsions that may not result in hospitalization; development of drug abuse or drug dependency.

Pregnancy: If a female subject or male subject's female partner inadvertently becomes pregnant while on treatment with pembrolizumab, the subject will immediately be removed from the study. The site will contact the subject at least monthly and document the subject's status until the pregnancy has been

completed or terminated. The outcome of the pregnancy will be reported to the IRB and to Merck within 10 days of the PI becoming aware of the outcome. If the outcome is a serious adverse experience (e.g., death, abortion, congenital anomaly, or other disabling or life-threatening complication to the mother or newborn), the PI upon learning of the event, will report to Merck.

The study investigator will make every effort to obtain permission to follow the outcome of the pregnancy and report the condition of the fetus or newborn to the IRB.

